Lastly, this study will evaluate a number of treatment approaches to HPV-related head and neck cancer. The approaches applicable to Cohort 1 of this study are outlined below:

1. Definitive chemoradiation without pretreatment surgical resection in which both the primary tumor site and the neck nodes receive 70Gy. In patients who exhibit a complete nodal response with this treatment, no further treatment is necessary.
2. Definitive chemoradiation without pretreatment surgical resection in which the primary site receives 70Gy while the neck nodes receive a lower dose of radiation at 60Gy instead of 70Gy. This definitive chemoradiation is followed by a FDG PET/CT scan at 3 months (+/- 4 weeks) post-treatment. In patients who exhibit a

complete nodal response with this method of treatment (as determined by the 3-month post-treatment FDG PET/CT scan), no further treatment is necessary.

Patients enrolled on to this protocol who will receive either of the treatments above (i.e. those without surgical resection of their cancer) will be included in Cohort 1, and will continue with standard institutional care in the case of incomplete or no nodal response. The information obtained from the use of ^{18}F -FMISO PET scans in Cohort 1 will be used to guide these patients' treatment on this protocol. HPV+ head and neck cancer patients in Cohort 1 that exhibit no evidence of hypoxia on their baseline ^{18}F -FMISO PET scan and HPV+ head and neck cancer patients in Cohort 1 with early resolution of hypoxia on their repeat ^{18}F -FMISO PET scan will receive 70Gy to the primary site and 60Gy to the neck nodes followed by a FDG PET/CT scan and observation.

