12.0 CRITERIA FOR THERAPEUTIC RESPONSE/OUTCOME ASSESSMENT

Not applicable.

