100 HPV+ patients with negative baseline scan or early resolution of tumor hypoxia of their node(s) at 5-10 treatment days into chemoradiation, defined by an absence or disappearance of ^{18}F -FMISO uptake on PET/CT, will achieve an equivalent nodal control with nodal radiation dose at 60Gy in the setting of chemotherapy with concomitant reduction in treatment-related complications. To test if patients receiving 60Gy to the node(s) followed by an FDG PET and observation similar treatment outcomes when compared to the radiation of 70Gy to the nodes both in the setting of concurrent chemotherapy, we will apply a one-sided one sample proportion test. Our past experience is that the nodal control rate at 3 months for such patient with 70Gy to the nodes is 94%. We will reject our hypothesis of equivalent control whether patients receive 70Gy to the nodes or 60Gy to the nodes followed by an FDG PET and observation if ≤ 57 patients out of the 66 in total who received 60Gy to the nodes achieve the same 3-month nodal control after chemoradiation. With this rule, we have a power of 0.93 for detecting that 60Gy will result in 3-month regional control lower than 80% with the type I error rate lower than 0.05. To test if patients receiving 60Gy to the nodes followed by an FDG PET and observation show superior toxicity outcomes when compared to the historical results from similar patients receiving 70Gy, we will apply a one-sided one sample proportion test. Grade 2 or higher toxicities that occurred within 3 months from the completion of IMRT will be counted in this analysis. Our past experience is that this toxicity rate for patients receiving 70Gy is around 75%. Using the total of 66 patients that undergo 60Gy to the nodes, we will reject our hypothesis of equivalent or higher toxicity rate when the nodes receive 10Gy less radiation from 70Gy when ≤ 43 patients have at least one \geq grade 2 toxicities. With this rule, we have a power of 0.84 for detecting the probability of 60% of patients will have at least one \geq grade 2 toxicity with the type I error rate lower than 0.05. Effort will be made to monitor all toxicities occurring beyond 3 months from chemotherapy and IMRT for all patients. However, censoring can be an issue so we will not apply the proportion test for toxicities after 3 months from chemoradiation. Instead, we will summarize the data descriptively and when applicable, we will use survival analysis tools such as Kaplan-Meier estimation and log-rank tests to determine whether 60Gy results in lower toxicity. To examine the potential correlations between various evaluation methods for nodal control status, we will apply a series of Fisher's exact tests.

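### Fisher's exact tests alone will not show how often two assessments of nodal control conflict, or whether one calls more failures

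*Combined protocol and SAP*

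**What the plan says.** The sentence at issue comes near the end of the Section 14.0 text on HPV-positive patients treated with 60Gy to the nodes. Its aim is to look for correlations between "various evaluation methods for nodal control status", and its whole method is "we will apply a series of Fisher's exact tests". Section 14.0 does not list the methods, and gives no alpha, sidedness, sample size or measure of strength for this series. The section headed "12.0 CRITERIA FOR THERAPEUTIC RESPONSE/OUTCOME ASSESSMENT" is marked as not applicable, so the methods are not defined there either. The one assessment of Cohort 1 nodal response that is named is in Section 1.0, where complete response is "as determined by the 3-month post-treatment FDG PET/CT scan".

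The same part of Section 14.0 holds the formal nodal-control rule. Equivalent control is rejected "if ≤ 57 patients out of the 66 in total who received 60Gy to the nodes achieve the same 3-month nodal control". The historical figure is that "the nodal control rate at 3 months for such patient with 70Gy to the nodes is 94" percent, and the plan states that "we have a power of 0.93 for detecting that 60Gy will result in 3-month regional control lower than 80" percent. No percent agreement, kappa or McNemar test is planned for the comparison of methods.

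**The concern.** The sentence is about several methods for one status. If two methods each label a patient as controlled or not, they can be cross-tabulated only as paired results. Methods aimed at the same status are expected to be associated, so rejecting independence says little. The useful questions are how many patients the methods classify differently, and whether the differences run in one direction. A Fisher p-value answers neither, and no descriptive measure is planned beside it.

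This has some practical weight because the 60Gy strategy ends in observation after a 3-month FDG PET/CT, and the 66-patient rule counts nodal control. A systematic difference between assessments would be worth seeing next to that count. A small Fisher p-value could be read as reassurance when such a difference exists.

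**Working it through.** **Inputs.** From Section 14.0: n=66, boundary 57, historical control 94%, so about 0.06 × 66 = 4 expected failures. Assumed, because the plan is silent: paired binary results and two-sided tests. The tables below are illustrations, not trial data.

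**Check of n and rate.** The plan gives no figure for the Fisher series, so the neighbouring rule was recomputed with X binomial (n=66).
- P(X ≤ 57 | 0.80) = 0.932; the plan states 0.93.
- P(X ≤ 57 | 0.94) = 0.017; the plan states below 0.05.

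Both reproduce.

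**Main illustration.** A calls 6 failures; B calls 20, including those 6.

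| | B failure | B controlled | Total |
|---|---|---|---|
| A failure | 6 | 0 | 6 |
| A controlled | 14 | 46 | 60 |
| Total | 20 | 46 | 66 |

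- Fisher: the probability that all 6 fall among B's 20 is C(20,6)/C(66,6) = 38,760/90,858,768 = 0.0004. No other table with these margins is as improbable, so this is the two-sided p.
- Overall agreement: (6+46)/66 = 52/66 = 79%, exact binomial 95% interval 67% to 88%. Discordant: 14 of 66.
- Agreement on failures: 2×6/(2×6+14) = 12/26 = 46%. Agreement on control: 2×46/(2×46+14) = 92/106 = 87%.
- Chance agreement: (6×20 + 60×46)/66² = 2,880/4,356 = 0.661. Kappa: (0.788 − 0.661)/(1 − 0.661) = 0.37.
- Exact McNemar: all 14 discordant pairs lie on one side, so p = 2 × 0.5^14 = 0.0001.
- Controlled counts: 66 − 6 = 60 by A and 66 − 20 = 46 by B. The first is above 57 and the second is below it.

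Fisher's result is correct as a statement of association. It says nothing about the 14 conflicts, all in one direction.

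**Limiting case.** With A calling 4 failures, compare perfect agreement (the same 4 called by B) with total disagreement (B calls exactly the other 62). Both have two-sided Fisher p = 1/C(66,4) = 1/720,720 = 1.4×10⁻⁶. The second table is unrealistic, but it shows that the p-value alone does not tell agreement from conflict.

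**Precision near 94% control.** If B also called all 4 of A's failures, the exact 95% interval for that 4 of 4 would run from 0.025^(1/4) = 40% to 100%. Any measure that rests on the failures will be imprecise.

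**The case against.** The strongest reply is that the plan asks about correlations, not agreement, and Fisher's test is a valid test of association. Section 14.0 uses the same form of words for FMISO imaging against HPV status, where association is plainly the aim. This stands, and it is why Fisher's tests need not be removed. It does not fill the gap for two classifications of one status, since a p-value does not measure the strength of an association either.

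Pairing is inferred, and this also stands. With the methods unlisted, the phrase "various evaluation methods for nodal control status" might extend to markers such as SUV or metabolic tumor volume. For a marker that predicts control, association is the right question, and McNemar or kappa would be the wrong tool.

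The main illustration gives B 20 failures, or 70% control, well below the expected 94%. That is fair: the table shows what Fisher's test leaves out and does not forecast the trial.

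A reader might also infer that Fisher's test can be non-significant when the methods agree well. Take 4 failures each with 1 in common: raw agreement is (1+59)/66 = 91% and Fisher p=0.23. But chance agreement is (4×4 + 62×62)/66² = 88.6%, kappa is 0.20, and agreement on failures is 2/8 = 25%. The high raw figure comes from shared non-failures, and Fisher's non-significance is not an error. McNemar gives p=1.00 there, so it too would miss the conflict; the discordant counts and agreement on failures would show it.

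Finally, a reader might want agreement against a reference standard. The documents define none for this comparison, and planned neck dissection applies only to Cohort 2 patients given 30Gy.

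**Conclusion.** The point holds in a limited form. For paired binary assessments of nodal control, Fisher's test alone leaves out the frequency and direction of conflict. In the illustration, p=0.0004 coexists with 14 of 66 patients classified differently and controlled counts of 60 and 46. This rests on two assumptions: that at least two of the unlisted methods classify the same patients, and that tests are two-sided.

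It would be wrong to infer that the 66-patient decision is unsound. The two counts show how large a difference could go unremarked. The control and toxicity rules do not use these Fisher tests, and no objective in Section 2.0 calls for a comparison of methods. The analysis is exploratory, and the change is a cheap improvement.

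**What to change.** In Section 14.0, list the evaluation methods and say which yield a controlled/not-controlled result in the same patients. For each such pair:

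- present the 2x2 table with both discordant counts;
- report overall, positive and negative agreement with 95% confidence intervals, using the symmetric forms shown above, which need no reference assessment;
- give the exact McNemar test for a systematic difference;
- give kappa only as a supplement, since it is unstable at about 94% control.

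Keep Fisher's exact test as a test of association, including for any predictive marker against control.

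The cost is a few sentences, which include defining the methods, and slight extra analysis of the same cross-tabulations. No further patients, visits or scans are needed. The downside is wide intervals with about four failures, which the report should state.

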2.0 OBJECTIVES

Primary

- To improve the accuracy of hypoxia imaging for head and neck cancers through pixel by pixel kinetic analysis of ^{18}F -FMISO tracer of dynamic PET images (Cohort 1 and Cohort 2).
- To detect on repeat ^{18}F -FMISO PET/CT scans whether there is a reduction of the ^{18}F -FMISO-avid or GIV_h 5 to 10 days into treatment with standard chemoradiotherapy for a series of locally advanced head and neck cancers (Cohort 1).
- To show that it is feasible to deliver 70Gy to primary site and 60Gy to the neck nodes in HPV+ patients who exhibit no evidence of hypoxia on their baseline ^{18}F -FMISO PET/CT scans or those who have early resolution of hypoxia on their early repeat ^{18}F -FMISO PET/CT scans (Cohort 1).
- To show that it is feasible to deliver 30Gy to the surgical bed and neck nodes in low-risk HPV+ patients who exhibit no evidence of hypoxia on their repeat ^{18}F -FMISO PET/CT (Cohort 2).
- To correlate the intensity of the ^{18}F -FMISO PET signal with the degree of immunohistochemical staining of hypoxia biomarkers for tissue obtained via biopsy (Cohort 1) and surgical resection (Cohort 2): HIF-1 α , Lysyl Oxidase, and Ki67 (an independent marker of tumor aggressiveness), among others.

Secondary

- To compare tumor heterogeneity derived from pixel-by-pixel kinetic analysis of PET scan and DWI-MRI (Cohort 1).
- To assess changes in tumor heterogeneity over the course of external beam RT using serial multiparametric MR and DCE-MRI scans (Cohort 1).
- To determine the potential of DCE-MRI data as a priori or early markers of tumor response to chemoradiation as well as long term disease-free survival after treatment (Cohort 1).
- To assess normal tissue response as a function of dose for parotid, submandibular glands, muscles and bones in the head and neck region during and after EBRT using serial multiparametric MR scans (Cohort 1).
- To bank specimens for further IRB/PB approved exploration of genetic analysis (Cohort 1 and Cohort 2).

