For Cohort 1 main campus patients, the follow-up MR scans, which will occur during concurrent chemoradiation, will last approximately 20-40 minutes. Information collected from all MR scans will not affect the standard of care, as baseline and post-treatment scans are currently a component of the standard of care. Additional scans will be acquired on our Philips 3T research scanner. Images will be sent to the research Pinnacle workstation for storage and evaluation. These images may be used for contouring of normal structures during the treatment planning process. DW-MRI images will be processed on the Philips research platform and corresponding diffusion and perfusion maps will be analyzed for therapy response assessment and treatment planning. Spatial changes during treatment will also be evaluated using functional diffusion maps or parametric response maps. No clinical decision will be made at this point based on MR findings.

PET/CT Image-guided Core Biopsy (Optional – Cohort 1 Patients Only)

The PET/CT scan will be performed in the Center for Image-Guided Intervention and Surgery at MSKCC, which houses a PET/CT scanner in an interventional radiology and operating room environment. The PET image-guided core biopsy procedure will be conducted as follows:

On the day of ^{18}F -FMISO PET/CT imaging, patients will be injected with the study tracer, ^{18}F -FMISO. After the final ^{18}F -FMISO PET image acquisition at each visit session (where applicable), biopsy samples will be removed from tumor tissue exhibiting high and low ^{18}F -FMISO uptake (if both are available). These high and low ^{18}F -FMISO uptake regions correspond to putative hypoxic and normoxic regions, respectively. Parametric image maps will also be retrospectively generated from compartmental models that define the rate of ^{18}F -FMISO radiotracer entrapment. These values will be used, in addition to the percent injected dose per gram, for correlation with IHC of hypoxia specific markers.

The aforementioned biopsy samples will be obtained by an interventional radiologist according to the features of the ^{18}F -FMISO PET/CT images. 1% lidocaine will be used for local anesthesia supplemented with midazolam and fentanyl citrate for light conscious sedation. The biopsy needle will be placed in position to remove core biopsy material of the node(s), and the patient will have an additional low dose CT to visualize the biopsy

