needle trajectory and location. In this way, we will obtain information of the exact location of the biopsy specimen in regard to the CT and therefore co-registered PET image. If movement should occur between biopsy localizer CT and the CT attenuation scan, then these two CT images will be co-registered using mutual information density software. Immediately following biopsy, the specimen will be properly oriented and pinned. Based upon published experience, discussion with other investigators, and our own experience of obtaining tissue prior and during treatment, we anticipate it will take approximately fifteen minutes to perform each biopsy. The specimen acquired from these tumor samples will be taken for paraffin embedding, fresh frozen (if patient consents to any of optional banking studies), and histological processing to our Pathology Department. Ten 5 μ m thick sections from paraffin tumor blocks or core samples will be deparaffinized and rehydrated, and stored at -80 °C until processing. IHC analyses will also be performed for the following hypoxia relevant biomarkers, among others: HIF-1 α , LOX, and Ki-67.

Pretreatment Surgical Resection (Cohort 2 Patients Only)

The eligible patient will undergo a pre-surgery FDG PET scan and an ¹⁸F-FMISO PET/CT scan. Following these pre-surgical scans, the patient will undergo his/her standard of care surgery. The surgeon will annotate the location of each sample resected from the lesion by a text description for documentation of relative position. The specimen will be embedded in paraffin in an orientation that will allow sectioning parallel to the imaging plane of the PET/CT image. Tissue sections will be stained with H&E, hypoxia specific, and proliferation markers using the same procedures as the described for the biopsy specimens in this protocol.

Biospecimen Samples

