
The spatial extent of ^{18}F -FMISO PET imaging within the neck node(s) determines the underlying hypoxia tumor phenotype for both HPV positive and negative HNSCC. To determine whether baseline ^{18}F -FMISO PET/CT and/or early-response ^{18}F -FMISO PET/CT at 5-10 treatment days after chemotherapy and IMRT correlate with selected proliferative/hypoxia molecular markers, Wilcoxon rank sum tests will be used for each marker. Multiple testing adjustments such as Bonferroni procedures will be used. To investigate whether the extent of ^{18}F -FMISO PET/CT measured hypoxia at baseline and/or 5-10 treatment days into chemoradiation for both HPV positive and negative tumors correlates with the development of distant metastasis, Kaplan-Meier estimates will be calculated for each stratum and compared using the log-rank tests. When competing risks are present, Gray's test will be used to examine the correlation between the extent of ^{18}F -FMISO PET/CT measured hypoxia with the development of distant metastasis. To examine the potential correlations between the baseline and early

response ¹⁸F-FMISO PET imaging and tumor's underlying HPV status, we will apply Fisher's exact tests.

Multiparametric scans will also be obtained. We will attempt comparisons to ¹⁸F-FMISO PET results and immunohistochemistry hypoxia results, but due to the small pilot size of this exploratory aim, we may not produce significant results. In that case, we will present summary statistics and suggest directions for future study.

> For this study cohort, 14 eligible patients will be needed for the analysis. Assuming approximately 25% of the patients enrolled will not be eligible, we will plan to recruit 19 patients upfront. For evaluation on the efficacy of the regimen in this cohort, a simple decision rule will be implemented, which is as follows: If, among the total 14 eligible patients, we have at least 10 patients who are alive, followed and have a pathologic CR at 4 months from the end of the treatment, then we will declare the treatment modality using 30 Gy is feasible and worthy of further investigation. Any patient who died or is lost to follow up within 4 months from the end of radiotherapy will be regarded as a failure, i.e., without pathologic CR. Feasibility for the primary objective in cohort 2 will be defined according to aforementioned decision rule. This decision rule has the following probabilities of declaring success.

True Locoregional Control Rate									

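### The FMISO-marker test is an unpaired rank-sum although one patient can supply several cores, and Section 14 states neither the unit of analysis nor the groups compared

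*Combined protocol and SAP*

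**What the plan says.** Section 2.0 lists as a primary objective, for both cohorts, "To correlate the intensity of the ^{18}F -FMISO PET signal with the degree of immunohistochemical staining of hypoxia biomarkers".

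The tissue comes from two sources.

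- **Cohort 1, optional core biopsy (Section 4.1, PET/CT Image-guided Core Biopsy).** After the last FMISO acquisition of a session, "biopsy samples will be removed from tumor tissue exhibiting high and low" uptake, on condition that both kinds of tissue can be found. The high and low "uptake regions correspond to putative hypoxic and normoxic regions, respectively". Schema items 1.8 and 1.13 and the Section 4.1 summary table allow a biopsy after the baseline scan and again after the repeat scan. One patient can therefore supply two cores at each of two sessions.
- **Cohort 2, resection (Section 4.1, Pretreatment Surgical Resection).** "The surgeon will annotate the location of each sample resected from the lesion", so a single lesion may also give several samples.

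On the imaging side, Section 4.1 describes continuous quantities from compartmental models and adds: "These values will be used, in addition to the percent injected dose per gram, for correlation with IHC of hypoxia specific markers".

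For the analysis, Section 14.0 asks whether baseline and/or early-response FMISO PET/CT is related to the selected markers, and answers that "Wilcoxon rank sum tests will be used for each marker", with a Bonferroni-type adjustment. It names no signed-rank test, random effect or clustered method for this question. It gives no unit of analysis, grouping variable, sample size, effect size or significance level.

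**The concern.** The rank-sum test compares two groups of independent observations. Cores from one patient are not independent: they share the patient's tumor biology, the scan session, and usually the processing and reading of the slides. The biopsy scheme was designed to set hypoxic against normoxic tissue within a patient, which is a paired or clustered structure. The one test named makes no use of it. The Bonferroni adjustment deals with the number of markers, not with dependence between specimens.

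Two things are at stake. The p-values for a primary objective could be too large or too small, depending on a choice the plan leaves open. And the tissue is scarce: Section 3.0 (Immunohistochemistry) reports that nearly half of the nearly 20 biopsy specimens obtained so far contained no tumor cells. Information lost in the analysis cannot easily be made up with more cores.

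**Working it through.** **Inputs.** The plan states no figure for this test, so there is none to reproduce. Assumed: normally distributed marker values, two-sided 0.05, and within-patient correlation ρ of 0.3, 0.5 or 0.7. Numbers of pairs and patients are also assumed. Simulations used 20,000 runs unless stated.

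**1. Cores as the unit, high versus low within the same patients.** The rank-sum takes the variance of the difference as if ρ were 0, but the true variance is smaller by the factor (1 − ρ). As a large-sample guide, true type I error ≈ 2·[1 − Φ(1.96/√(1 − ρ))].

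| ρ | formula | rank-sum, 20 pairs | signed-rank, 20 pairs |
|---|---|---|---|
| 0.3 | 1.96/√0.7 = 2.34 → 0.019 | 0.021 | 0.048 |
| 0.5 | 1.96/√0.5 = 2.77 → 0.006 | 0.008 | 0.051 |
| 0.7 | 1.96/√0.3 = 3.58 → 0.0003 | 0.002 | 0.049 |

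The test is too strict. With all 20 pairs complete and an assumed high-low difference of 0.6 SD, rank-sum power is 0.43/0.41/0.41 against 0.56/0.70/0.89 for signed-rank.

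**2. Cores as the unit, several from one patient in the same group.** This arises if patients are grouped by scan result and every core is counted. The variance is now understated by the factor 1 + (k − 1)ρ for k cores per patient, so true type I error ≈ 2·[1 − Φ(1.96/√(1 + (k − 1)ρ))]. Simulation with 10 versus 10 patients:

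| ρ | k = 2: formula | k = 2: simulated | k = 4: formula | k = 4: simulated |
|---|---|---|---|---|
| 0.3 | 1.96/√1.3 = 1.72 → 0.086 | 0.087 | 1.96/√1.9 = 1.42 → 0.155 | 0.151 |
| 0.5 | 1.96/√1.5 = 1.60 → 0.110 | 0.110 | 1.96/√2.5 = 1.24 → 0.215 | 0.214 |
| 0.7 | 1.96/√1.7 = 1.50 → 0.133 | 0.134 | 1.96/√3.1 = 1.11 → 0.266 | 0.269 |

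The test is too lenient.

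**3. One value per patient, different patients in each group.** Simulated type I error is 0.042 to 0.044. The test is valid, but the high-low contrast is not used.

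**4. Allowing for cores without tumor cells.** Suppose each core is evaluable independently with probability 0.5. A patient then yields a complete pair with probability 0.25, one core with 0.50 and none with 0.25. Of 40 biopsied patients, about 10 give pairs and 20 give single cores, so two-thirds (0.50/0.75) of those with any evaluable core have only one. On all evaluable cores, high versus low, rank-sum type I error is 0.036/0.027/0.016 (4,000 runs). Power for an assumed 0.8 SD shift (2,500 runs), at ρ = 0.3/0.5/0.7:

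| patients | rank-sum, all cores | signed-rank, complete pairs |
|---|---|---|
| 28 | 0.48/0.50/0.50 | 0.23/0.32/0.45 |
| 40 | 0.65/0.69/0.69 | 0.42/0.56/0.72 |

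The signed-rank test loses in five of the six settings. In a separate run of these settings, a random-patient-effect model on all cores had power 0.60 to 0.81 (28 patients) and 0.76 to 0.93 (40 patients), against 0.47 to 0.50 and 0.67 to 0.69 for the rank-sum. Its type I error without small-sample correction was 0.06 to 0.08, so part of that gain would go once it is corrected.

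**The case against.** The strongest reply is that Section 14.0 never proposes comparing high with low cores. The paragraph opens with the spatial extent of FMISO uptake in the neck nodes and asks about baseline and early-response scans, which reads naturally as one scan-level value per patient. On that reading the rank-sum is valid (step 3). This stands: a reader might infer that the planned test simply has the wrong error rate, and the documents do not support that. It does not close the point. The plan never says that cores are reduced to one value per patient, nor how, and doing so sets aside the contrast that the biopsy scheme was built to collect.

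A second reply is that pairs may be few. Biopsy is optional and confined to Cohort 1, low-uptake cores depend on availability, and surgical specimens were added because needle sampling failed so often. This stands too. It rules out two further inferences: that a plain signed-rank test is the remedy, and that the gain seen with complete pairs would be realized. Step 4 contradicts both.

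Third, where high and low cores are compared, the error is conservative: power is lost, and false positives are not added. Inflation needs several same-patient cores counted in one group, which nothing in the plan prescribes, although nothing excludes it.

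Finally, one might argue that sampling the extremes of uptake would exaggerate a pooled correlation coefficient. Section 14.0 names no such coefficient and Section 4.1 gives no percentile rule for choosing cores, so that criticism has no stated analysis to attach to.

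**Conclusion.** The point holds in a limited form. The plan names a test for independent groups, collects specimens that can be paired and clustered within patients, and leaves the unit of analysis and the groups open. Depending on that choice, nominal 0.05 becomes about 0.02 to 0.002 (high versus low, complete pairs) or about 0.09 to 0.13 (two cores per patient in one group), or stays near 0.05 with the within-patient information unused.

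These sizes rest on assumed correlations, normal marker values and assumed numbers of patients. The directions follow from the variance factors and do not depend on the exact values. It should be corrected because the objective is primary and tissue is scarce. It does not touch the 60Gy or 30Gy decision rules, which use other endpoints.

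**What to change.** In Section 14.0:

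1. State the unit of analysis and the groups or exposure compared for each marker, for biopsy cores and for resected samples.
2. Where specimens are the unit, replace the rank-sum with a patient-clustered method that keeps both pairs and single cores: a random patient effect with a small-sample correction, or a clustered rank test.
3. Report the signed-rank test on complete high-low pairs as a sensitivity analysis only.
4. Where patients are compared with each other, use one value per patient and visit, and say how it is derived from several cores. The rank-sum can stay for that comparison.

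This needs wording only: no further patients, tissue or procedures. The price is a slightly more complex analysis and some dependence on a model in a small sample. The small-sample correction is needed, since the uncorrected model ran at 0.06 to 0.08 in the check above.
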